## 5.2. Week 24 (DB Period) Final Analysis

The final unblinded analysis of the double-blind, placebo-controlled period will be conducted once all subjects have had the opportunity to complete the Week 24 visit. Data through Week 24, including the primary, key secondary, secondary, and exploratory endpoints, will be analyzed. At this time, an analysis of all available safety and efficacy data through Month 12 will also be performed. Following this analysis, the subject, investigator, all study center personnel, and Sponsor personnel with direct contact with the site will continue to be blinded to the subject's blinded treatment assignment. All planned analyses for the final Week 24 analysis are included in this SAP.

### **5.3. Month 12 (OL Period) Final Analysis**

The final analysis of the open-label period will be conducted once all subjects have had the opportunity to complete the Month 12 visit. At this time, all data collected up to Month 12 will be analyzed. All planned analyses for the final Month 12 analysis are included in this SAP.

## **6. GENERAL CONSIDERATIONS FOR DATA ANALYSES AND HANDLING**

### **6.1. General Statistical Procedures**

All analyses described in this plan are considered a priori analyses in that they have been defined prior to locking the study database for the Week 24 analysis. Analyses defined subsequent to locking the database will be considered post hoc analyses and will be applied as exploratory methodology. Any post hoc analyses will be statistically justified and described as appropriate in the CSR. Statistical analysis will be conducted, and all tables, figures, and listings generated using SAS® software (version 9.4 or later), unless stated otherwise.

Unless otherwise noted, data from the double-blind, placebo-controlled period (Day 1 to Week 24; “DB period”) will be summarized by randomized treatment group at Day 1, defined as placebo or crinecerfont 100 mg bid (DB treatment group). Data from the open-label period (Week 24 to Month 12; “OL period”) will be summarized by OL treatment group, defined as placebo/crinecerfont 100 mg bid or crinecerfont 100 mg bid/crinecerfont 100 mg bid to describe their randomized treatment assignment at Day 1 and their OL treatment, as well as all subjects combined.

Descriptive and inferential statistical methods will be used to evaluate and summarize the data from this study. The term “descriptive statistics” refers to the number of subjects (n), mean, median, standard deviation (SD) or standard error (SE), minimum, and maximum for continuous variables. Ordinal categorical data will be summarized using median, minimum and maximum values. Number and percentage of subjects will be summarized for categorical variables. The term “inferential statistics” refers to hypothesis tests that will be performed to assess differences between the treatment group and the control group. All hypothesis tests will be tests of the null hypothesis of no difference between the groups being compared versus the two-sided alternative hypothesis that there is a difference. The level of significance (type I error) for declaring statistical significance will be 0.05.

Summary statistics will be presented using the following decimal precision (ie, number of digits to the right of the decimal point): the minimum and maximum will have the same number of decimal places as the data; the mean, median, SD and SE will have one more decimal place than the data being summarized; the sample size (N) will be reported as an integer; with the exception of 100 percent, percentages will be reported to one decimal place (percentages for zero counts are omitted); and p-values will be displayed using four decimal places. Confidence intervals for means will be reported to the same number of decimal places as mean values; and confidence intervals for percentages will be reported to one decimal place. These rules may be modified if warranted, based on practical considerations.

All available study data will be included in relevant data displays, including data for subjects with incomplete or missing values. Replacement of missing data values with imputed values will generally not be performed unless specified otherwise in relevant endpoint subsections.

## 6.2. Analysis Sets

**Table 1: Definitions of Analysis Sets**

Analysis Set	Description
Full Analysis Set	The full analysis set (FAS) will include all randomized subjects. Subjects will be analyzed according to their randomized treatment group, regardless of adherence to study drug administration.
Full Analysis Set Excluding Site No. 1083	The FAS as defined above, excluding subject data for site 1083.
DB Period Safety Analysis Set	The safety analysis set (SAS) will include all randomized subjects who take at least 1 dose of study drug in the double-blind period. Subjects will be analyzed according to their randomized treatment group, unless they receive the incorrect study drug for the entire double-blind treatment duration.
OL Period Safety Analysis Set	The safety analysis set (SAS) will include all subjects who take at least 1 dose of active study drug (crinecerfont) during the open-label period.
PK Analysis Set	The PK analysis set (PKAS) will include all subjects randomized to crinecerfont who take at least 1 dose of study drug and have at least one post-dose PK concentration.

### 6.2.1. Application of Analysis Sets

Summaries of subject disposition, analysis set inclusion/exclusion status, and protocol deviations will include all randomized subjects for the DB period. Summaries of subject disposition and protocol deviations in the OL period will use the OL period safety analysis set. The summary of analysis set inclusion/exclusion status summary in the OL period will include all randomized subjects. Analysis sets used for all other summaries are defined at the beginning of each major section.

Analyses for the primary efficacy and all key secondary efficacy endpoints will be re-run using the FAS excluding site number 1083 analysis set.

## 6.3. Baseline Definitions

The following sections describe the baseline definitions used in the DB and OL periods, as well as baseline definitions specifically defined for the primary and key secondary efficacy endpoints. For each subject, study day is calculated relative to Day 1, where Day 1 is defined as the date of first dose of study drug.

### **6.3.1. Baseline Definition for Analyses of DB Period Data**

Other than the definitions described in Sections 6.3.3 through 6.3.5, the assessments collected on Day 1 prior to the first dose of study drug in the DB period will serve as the baseline value for all assessments through Week 24 of the study. If a Day 1 baseline value is not available, then the last measurement collected prior to study drug will serve as baseline. Body composition assessments obtained within 2 weeks after Day 1 may serve as the baseline if needed. Bone mineral density and testicular ultrasound assessments obtained within 1 month after Day 1 may serve as the baseline value if needed, as these parameters are not expected to change to a degree that could be clinically detected over this time frame. Note that for hormone parameters that are collected both pre- and post-glucocorticoid (GC) dose, baselines will be defined as the last pre- or post-GC dose value available prior to study drug dosing for all pre- and post-GC dose postbaseline values, respectively, where a change from baseline calculation is necessary, unless otherwise specified.

### **6.3.2. Baseline Definition for Analyses of OL Period Data**

Two baselines will be defined for analyses of data from the OL period. For all efficacy summaries in the OL period, the Week 24 assessments collected prior to the first dose of study drug in the OL period will serve as one of the baseline values for assessments through Month 12 of the study. This baseline will be referred to as the “OL baseline” throughout this document. Unless otherwise noted, all efficacy summaries will be repeated using the study baseline (as defined in Section 6.3.1). For both the OL baseline and study baseline, if the respective Week 24 or Day 1 value is not available, then the last measurement collected prior to study drug in each period will serve as baseline. Specifically, for the OL period, if the Week 24 value is not available, then the last measurement collected prior to study drug in the OL period will serve as baseline as long as the last non-missing measurement is not the study baseline value. For assessments that are performed every 6 months, if the Week 24 assessment is not available then the OL baseline and postbaseline values will not be included in the summary.

Body composition assessments obtained within 2 weeks after Week 24 may serve as the OL baseline if needed. Bone mineral density and testicular ultrasound assessments obtained within 1 month after Week 24 may serve as the OL baseline value if needed, as these parameters are not expected to change to a degree that could be clinically detected over this time frame.

Note that for hormone parameters that are collected both pre- and post-GC dose, OL baselines will be defined as the last pre- or post-GC dose value available prior to study drug dosing at Week 24 for all pre- and post-GC postbaseline values (after Week 24), respectively, where a change from OL baseline calculation is necessary, unless otherwise specified.

### **6.3.3. Baseline Definition of Androstenedione “Control” for Primary and Second Key Secondary Endpoints**

At Day 1 and Week 24, a sample for serum androstenedione is collected before the morning glucocorticoid dose (pre-GC dose) and 2 hours after the morning glucocorticoid dose (post-GC dose). Subjects not on a morning glucocorticoid dose had two samples collected 2 hours apart with the second sample collected before 1100 hours on Day 1 and Week 24. The Week 24 samples were also timed to be collected prior to and 2 hours after the morning study drug dose.

The post-GC dose androstenedione values at Day 1 will be considered the baseline value for the purpose of assessing androstenedione control at Week 24 (also using the post-GC dose value) as part of the primary endpoint of GC dose reduction while maintaining androstenedione control. If the Day 1 value is missing, the last post-GC dose androstenedione value collected prior to Day 1 will serve as the baseline. If a subject is missing their Week 24 post-GC dose androstenedione value, then the pre-GC dose androstenedione values at Day 1 and Week 24 will be used instead. If both pairs of pre- and post-GC androstenedione values at Day 1 and Week 24 (ie, pre-GC dose Day 1/pre-GC dose Week 24 and post-GC dose Day 1/post-GC dose Week 24) are incomplete, then the androstenedione values (for the purpose of the Week 24 endpoint of GC dose reduction with androstenedione control) at Week 24 will be considered missing and will be imputed using the missing data handling approach described in the primary efficacy analysis of this endpoint (Section 9.3.1). If a subject is missing their Week 24 post-GC dose androstenedione value but has a Week 24 pre-GC dose androstenedione value that is  $\leq$  ULN based on age and sex, then the subject will be considered in androstenedione “control.” Note that if all Week 24 androstenedione values are missing, the subject will still have an androstenedione value assigned as baseline. This baseline value will be defined as the last post-GC value prior to study drug dosing. If there are no post-GC values available prior to study drug dosing, then the last pre-GC dose value prior to study drug dosing will be used instead. If a subject is missing all androstenedione values prior to study drug dosing, then their baseline androstenedione value will be multiply imputed using the methodology described in Section 16.1.

This same method of determining the baseline and corresponding Week 24 androstenedione values used to assess control will also be applied to the second key secondary endpoint, the achievement of a reduction in glucocorticoid daily dose to physiologic levels ( $\leq 11$  mg/m^2/day hydrocortisone equivalents adjusted for BSA) while androstenedione is controlled at Week 24. The missing data handling approach is described in Section 9.4.2.

#### **6.3.4. Baseline Definition of Androstenedione for First Key Secondary Endpoint**

The first key secondary endpoint is the change from baseline to Week 4 in serum androstenedione based on the pre-GC dose androstenedione values at Day 1 and Week 4. If a subject is missing the Week 4 pre-GC dose androstenedione value, then the post-GC androstenedione values at Day 1 (or last post-GC dose androstenedione value prior to Day 1, if Day 1 is missing) and Week 4 will be used instead. If both pairs of pre- and post-GC androstenedione values at Day 1 and Week 4 (ie, pre-GC dose Day 1/pre-GC dose Week 4 and post-GC dose Day 1/post-GC dose Week 4) are incomplete, then the androstenedione values (for the purpose of the Week 4 androstenedione endpoint) at Week 4 will be considered missing and will be imputed using the missing data handling approach described in primary efficacy analysis method for this endpoint (Section 9.4.1). The last pre-GC dose androstenedione value prior to study drug dosing will be used as the baseline if all Week 4 values are missing. If there are no pre-GC values available prior to study drug dosing, then the last post-GC dose value prior to study drug dosing will be used instead. If a subject is missing all androstenedione values prior to study drug dosing, then their baseline androstenedione value will be multiply imputed using the methodology described in Section 16.2.

### 6.3.5. Baseline Definition of 17-OHP for Secondary Endpoint

Change from baseline to Week 4 in serum 17-OHP is a secondary endpoint. The same method as described in Section 6.3.4 will be followed for the purpose of determining baseline and Week 4 17-OHP values for this endpoint. Note that missing values will not be multiply-imputed.

## 6.4. Completers, Retrieved Dropouts, Non-Retrieved Dropouts, and On Drug-Missing Endpoint Subjects

The methods of multiply imputing missing data require classifying subjects based on having evaluable measurements and their treatment status at the time of the endpoint (namely, Week 4 or Week 24). For the purpose of missing data imputation, the following types of subjects are defined in the table below.

**Table 2: Evaluability of Subjects at Endpoint**

Subject Classification	Description
Completers	Subjects in the FAS who completed through the time of the endpoint (Week 4 or Week 24, as applicable) on study drug and have an evaluable measurement for that endpoint. For endpoints with more than one data component, the subject must have complete data for all components of the endpoint.
Retrieved Dropouts	Subjects in the FAS who discontinue study drug prior to the time of the endpoint collection but remain in the study and have an evaluable measurement for that endpoint. For endpoints with more than one data component, the subject must have complete data for all components of the endpoint.
Non-retrieved Dropouts	Non-retrieved dropouts are subjects in the FAS who discontinue from the study and from study drug and do not have an evaluable measurement for that endpoint.
On Drug-Missing Endpoint	Subjects in the FAS who are on study drug at the time of the endpoint but do not have an evaluable measurement for that endpoint.

## 6.5. Hormone Reference Ranges

The appropriate reference ranges for androstenedione, 17-hydroxyprogesterone, and progesterone in adult female subjects are dependent on the female subject's pre- or post-menopausal status at Day 1 and are shown in [Table 3](#). For males, the reference ranges are dependent on age and the reference ranges are also given in [Table 3](#). For the purposes of analysis, female subjects who are postmenopausal will have their postmenopausal status marked in their medical history. Female subjects who are postmenopausal will use the "postmenopausal phase" reference ranges provided by the central laboratory. All other female subjects will use the "pre-menopausal mid-follicular" reference ranges provided by the central laboratory.

Reference ranges are also given by sex for ACTH, follicle stimulating hormone (FSH), luteinizing hormone (LH), sex hormone binding globulin (SHBG), and total testosterone.

The assignment of these hormone reference ranges will apply to all summaries and analyses that use reference ranges.

**Table 3: Hormone Reference Ranges**

Hormone Reference Ranges	
Lab Analyte	Reference Ranges: conventional units; SI units
Androstenedione (conversion factor from ng/dL to nmol/L: x 0.0349)	
Adult Male:
 
18-30 years: 50-220 ng/dL; 1.745 - 7.678 nmol/L
 
31-50 years: 40-190 ng/dL; 1.396 - 6.631 nmol/L
 
51-60 years: 50-220 ng/dL; 1.745 - 7.678 nmol/L
 
Adult Female:
 
Mid Follicular: 51-213 ng/dL; 1.7799 - 7.4337 nmol/L
 
Surge: 73-230 ng/dL; 2.5477 - 8.027 nmol/L
 
Mid Luteal: 73-184 ng/dL; 2.5477 - 6.4216 nmol/L
 
Postmenopausal: 20-75 ng/dL; 0.698 - 2.6175 nmol/L

17-OH Progesterone (17-OHP) (conversion factor from ng/dL to nmol/L: x 0.0303)	
Adult Male:
 
18-30 years: 32-307 ng/dL; 0.9696 - 9.3021 nmol/L
 
31-40 years: 42-196 ng/dL; 1.2726- 5.9388 nmol/L
 
41-50 years: 33-195 ng/dL; 0.9999 - 5.9085 nmol/L
 
51-60 years: 37-129 ng/dL; 1.1211 - 3.9087 nmol/L
 
>= 61 years: Not established
 
Adult Females:
 
Pre-menopausal mid follicular: 23-102 ng/dL; 0.6969 - 3.0906 nmol/L
 
Pre-menopausal surge: 67-349 ng/dL; 2.0301-10.5747 nmol/L
 
Pre-menopausal mid luteal: 139-431 ng/dL; 4.2117 - 13.0593 nmol/L
 
Post-menopausal phase: <=45 ng/dL; 1.3635 nmol/L

Progesterone (conversion factor from ng/mL to nmol/L: x 3.18)	Male: <0.15ng/mL; 0.477 nmol/L, <0.48 nmol/L; 1.5264 nmol/L  Female: Premenopausal, not pregnant: <23.90 ng/mL, <76 nmol/L Female, pregnant: 11.00 – 214 ng/mL, 34.98 - 680.52 nmol/L Female, postmenopausal: <0.13 ng/mL, <0.41 nmol/L
ACTH (conversion factor from pg/mL to pmol/L: x 0.22)	Males and Females: 7.2 – 63.3 pg/mL; 1.584 -13.926 pmol/L
Follicle stimulating hormone (FSH) (conversion factor from mIU/mL to IU/L: x 1.0)	Male: 1.6 - 11.0 mIU/mL (IU/L) Female: 1.8 - 20.4 mIU/mL (IU/L)
Luteinizing Hormone (LH) (conversion factor from mIU/mL to IU/L: x 1.0)	Male: 1.7 - 8.6 mIU/mL (IU/L) Female: 1.0 - 95.6 mIU/mL (IU/L)
Sex Hormone Binding Globulin (SHBG)	Male: 10.0 - 80.0 nmol/L (same in SI) Female: 20.0 - 130.0 nmol/L (same in SI)
Total Testosterone (Medpace/MRL) (conversion factor from ng/mL to nmol/L: x 3.47)	Male: 2.70- 10.70 ng/mL; 9.37-37.13 nmol/L Female: 0.06 - 0.86 ng/mL; 0.21-2.98 nmol/L
Total Testosterone (Quest) (conversion factor from ng/dL to nmol/L: x 0.0347)	Male: 250 - 1100 ng/dL; 8.675 - 38.17 nmol/L Female: 2 - 45 ng/dL; .0694 - 1.5615 nmol/L

## 6.6. Derived and Transformed Data

Change from baseline is calculated as the postbaseline value minus the baseline value; a negative value will represent a decrease at the postbaseline visit. Percent change from baseline is calculated as:  $\text{change from baseline}/\text{baseline value} \times 100$ . If either the baseline or postbaseline value is missing, the change from baseline and/or percent change from baseline will also be missing. The percent change from baseline will also be missing if the baseline value is equal to 0.

With the exception of pharmacokinetic concentration data, all below the lower limit of quantification (BLQ) values will be set equal to the BLQ value in all summaries. For values that are above the upper limit of quantification (ULQ), the value will be set equal to the ULQ.

## 6.7. Study Day

For each subject, study day is calculated relative to Day 1, where Day 1 is defined as the date of first dose of study drug. If the date of interest occurs on or after Day 1, then the study day will be calculated as: date of interest – date of Day 1 + 1. If the date of interest occurs prior to Day 1, then the study day will be calculated as: date of interest – date of Day 1. For subjects who are randomized but never dosed, Day 1 will be defined as the subject's randomization date.

The nominal visit number for each visit, including scheduled, unscheduled, repeat, and early termination/end of study visits, will be re-mapped to an analysis visit according to [Table 4](#), [Table 5](#), [Table 6](#), [Table 7](#), [Table 8](#). If multiple measurements occur within the same visit window after mapping, the measurement that is closest to the target study day will be used for the summary tables where one observation per visit is needed, unless otherwise specified. Where there are ties between the earlier and later observation within the visit window, the earlier observation will be used. For the purpose of this study, months are defined as 4-week intervals.

The primary endpoint of percent change from baseline in glucocorticoid daily dose at Week 24 is based on the glucocorticoid concomitant medications eCRF. The method of collecting concomitant medication data involves entering a start date and stop date for each medication, unless it is ongoing, in which case the “Ongoing?” field is marked as “yes.” This differs from assessments that are collected discretely at visits. Additionally, the androstenedione values collected at the Week 24 visit are a critical component to the assessment of this endpoint as subjects who do not maintain androstenedione control will have their percent change from baseline value in glucocorticoid total daily dose set to 0. For the purposes of determining the glucocorticoid total daily dose from the eCRF at Week 24, the Week 24 visit date at which the androstenedione values were collected (based on the analysis visit mapping described below) will be used to determine the glucocorticoid dose (as of the same date) to be used for the primary endpoint. If a subject has a Week 24 visit performed based on the analysis visit window but androstenedione was not collected at this visit (ie, missed hormone labs), then the analysis visit date from the collection of the safety labs will be used instead for determining the Week 24 glucocorticoid total daily dose. If both hormone and safety labs were missed at the visit, then the vital signs assessment and its respective Week 24 analysis visit date will be used for determining the glucocorticoid total daily dose. The same methodology described above will be used to determine the glucocorticoid total daily dose from the eCRF at each of the other intermediate visits.

[Table 4](#) includes the analysis visit windows for all assessments, with the exception of those assessments that have a broader window due to more infrequent assessments (eg, every 6 months). These more-infrequent assessments include measurements obtained via DXA (bone mineral density and body composition), testicular ultrasound measurements, HbA1c, glucose tolerance test, insulin, bone markers, and lipid panel. These assessments will use the analysis visit windows defined in [Table 6](#), [Table 7](#), and [Table 8](#), as applicable. [Table 5](#) includes the analysis visit windows for subjects who discontinue from study drug prior to OL period or OL/DB period and therefore do not have a first dose date in the OL period or OL/DB period.

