9.3. Efficacy Assessments

9.3.1. Glucocorticoid Dosing and Dose Reduction

Each subject will record their daily glucocorticoid regimen in the eDiary beginning at Screening Visit 1, including specific type of glucocorticoid and all doses taken each day for their usual regimen as well as any additional or sick-day dosing ([Appendix B](#)). The usual daily regimen will be converted to hydrocortisone equivalents ($\text{mg}/\text{m}^2/\text{day}$) adjusted for BSA (see [Appendix A](#)).

Guidelines for reducing or optimizing glucocorticoid dose should be followed in order to evaluate the efficacy of the study drug, except in the event that a subject requires sick-day dosing. Sick-day dosing may follow guidelines outlined in Appendix B or be based on guidance provided by the investigator or their treating physician. If a subject's glucocorticoid regimen is adjusted due to sick-day guidelines, the subject should resume their glucocorticoid dosing regimen (according to their glucocorticoid reduction schedule) for at least 3 days before their next scheduled hormone panel assessment. Of note, this 3-day window supersedes all other visit windows.

Glucocorticoid Dose Reduction during Placebo-Controlled Period

The goal of the glucocorticoid dose reduction period from Week 4 to Week 12 is to reach the subject's target physiologic dose of 8 to 10 $\text{mg}/\text{m}^2/\text{day}$ (hydrocortisone equivalents adjusted for BSA) within 4 or fewer steps by Week 12, unless the subject has any signs or symptoms suggestive of clinically relevant glucocorticoid insufficiency or unacceptable symptoms of hyperandrogenism, as outlined below. However, before the glucocorticoid dose reduction is stopped for symptoms or signs of orthostatic hypotension, volume status should be optimized (eg, with additional dietary salt, salt tablets, intravenous saline).

- Unexplained hyponatremia (serum sodium $<135 \text{ mmol/L}$)
- Orthostatic hypotension with decrease in systolic blood pressure $>20 \text{ mmHg}$ or in diastolic blood pressure $>10 \text{ mmHg}$ after standing (from a seated position) after

- approximately 2 minutes, or severe symptoms of dizziness or lightheadedness upon standing
- Severe nausea, food aversion, vomiting
- Unacceptable symptoms of hyperandrogenism (eg, hirsutism, acne, amenorrhea)

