9.3.2. Hormone Panel

At all study visits (including screening) except Week 8 and Week 10, a blood sample should be collected for hormone measurements in the morning approximately 2 to 3 hours after the morning glucocorticoid dose (and fludrocortisone dose if taking) is taken. Additional blood samples for hormone measurements may be collected at unscheduled visits if clinically indicated.

In addition, a predose blood sample for hormone measurements prior to the morning glucocorticoid dose (and fludrocortisone dose if taking) will be collected at Day 1 (baseline),

Weeks 4 and 24, and Months 12, 13 (for subjects re-randomized at Month 12), 18, 24, and every 12 months thereafter. At these visits, subjects will hold their morning glucocorticoid dose until arriving at the study site so that a blood sample for hormone measurements can be collected. Subjects will then take their morning dose of glucocorticoid (and fludrocortisone dose if taking) at the study site, with another blood sample collected approximately 2 hours later. The second (2-hr postdose) blood sample should be collected prior to 1100 hours. Subjects not on a morning glucocorticoid should still have 2 morning blood samples taken (eg, with the glucose tolerance test at Day 1, Week 24, Month 12, etc.; and/or before and 2 hours after the morning study drug dose). Additional plasma or serum hormone levels may be evaluated using the second blood sample collected at these timepoints.

The hormone panel will include assessment of:

- Adrenal androgens and precursors (ACTH, 17-OHP, cortisol, androstenedione, testosterone) and sex hormone binding globulin (only for the second blood sample collected at Day 1, Weeks 4 and 24, and Months 12, 13, 18, 24, and every 12 months thereafter)
- Reproductive function (luteinizing hormone [LH], FSH, progesterone)
- Mineralocorticoid status (upright PRA)

The blood samples will be processed and stored according to the procedure as specified in the laboratory manual.

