### 9.3.2. Primary Efficacy Analysis

The primary efficacy endpoint is the percent change from baseline in glucocorticoid daily dose (in hydrocortisone equivalents adjusted for BSA [mg/m^2/day]) at Week 24, while Week 24 androstenedione is adequately controlled at  $\leq 120\%$  of baseline or  $\leq \text{ULN}$  for age and sex.

Glucocorticoid daily dose will be calculated at baseline (as defined in Section 6.3.1) and at Week 24 using the doses reported on the glucocorticoid medications eCRF (see details in Section 6.7 regarding mapping of the glucocorticoid medication to Week 24). Glucocorticoids other than hydrocortisone will be converted to hydrocortisone equivalents using the equivalency factors defined in Appendix A of the study protocol and Section 16.3. BSA will be calculated using the height from the screening visit and weight from the Day 1 visit, computed using the DuBois formula (Section 7.3). If glucocorticoid dosing alternates over the course of two consecutive days, then the average of the glucocorticoid dose on those days will be used to calculate the glucocorticoid daily dose. If glucocorticoid dosing alternates between weekdays and weekends (or another weekly regimen that varies by day of the week), then the average daily dose will be calculated as the sum of the glucocorticoid doses over the 7-day period divided by 7.

Baseline androstenedione will be defined as the Day 1 post-morning glucocorticoid dose androstenedione value. Further details of the derivation of this baseline value are described in Section 6.3.3.

Subjects who have a decrease in glucocorticoid daily dose but do not meet the definition of androstenedione control at Week 24 will be considered to have a zero percent change from baseline in the glucocorticoid daily dose at Week 24. Any increases from baseline in glucocorticoid daily dose will be reported as such, regardless of androstenedione control.

Subjects who are missing Week 24 glucocorticoid dose data or all Week 24 androstenedione levels will have their data imputed through the multiple imputation procedures described in Section 16.1.

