## **13. DEVIATIONS FROM PROTOCOL PLANNED ANALYSIS**

This section will document any deviations from the protocol planned analysis along with any assessments that were performed on study (and reviewed by the study site) but will not be summarized.

The following assessments were performed or collected on study but will not be summarized:

- Physical examination results (excluding waist circumference, weight, height)
- CYP21A2 genotyping
- Pregnancy test
- Urine drug screen
- Urinalysis
- Testicular ultrasound – locally read data
- Glucocorticoid dose diary data

The following list includes all deviations from the protocol planned analysis:

- The Safety Analysis Set definition in the protocol specified that the subject must have postbaseline safety data during the double-blind placebo-controlled period. This part of the definition was removed from the SAP due to the potential issue of having a subject dosed with study drug and then becoming lost to follow-up.

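### The Week 24 visit mapping has no sick-day check, so an androstenedione sample drawn under stress dosing can displace the protocol-compliant one and misclassify control

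*SAP*

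**What the plan says.** Protocol 9.3.1 keeps sick-day steroid apart from background steroid in two ways. On dose: "The usual daily regimen will be converted to hydrocortisone equivalents". On sampling, a subject who has used sick-day dosing should be back on the regimen "for at least 3 days before their next scheduled hormone panel assessment", and this 3-day window overrides all other visit windows. Protocol 9.3.2 adds: "Additional blood samples for hormone measurements may be collected at unscheduled visits if clinically indicated".

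The SAP restates neither safeguard. On mapping, SAP 6.7 says: "The nominal visit number for each visit, including scheduled, unscheduled, repeat, and early termination/end of study visits, will be re-mapped to an analysis visit". It then gives the selection rule: "If multiple measurements occur within the same visit window after mapping, the measurement that is closest to the target study day will be used". Ties go to the earlier sample. The Week 24 target is Day 168 and the window runs from Day 155 to the first open-label dose (SAP Table 4). For the primary endpoint, the date of the mapped Week 24 androstenedione sample "will be used to determine the glucocorticoid dose (as of the same date) to be used for the primary endpoint". SAP 9.3.2 computes the dose "using the doses reported on the glucocorticoid medications eCRF", with special rules only for alternate-day and day-of-week regimens.

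SAP 6.3.3 judges control on the post-dose sample, with the pre-dose pair as fallback, and applies the same method to the responder endpoint (also SAP 9.4.2). Sick-day dosing is not among the four intercurrent events in SAP 9.3.1. It appears only in the safety tables of SAP 11.2.4. SAP 13 lists "Glucocorticoid dose diary data" among items collected but not summarized.

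**The concern.** The 3-day rule exists so that androstenedione reflects the usual regimen and not a temporary surge of hydrocortisone. A site honours it by moving the Week 24 visit later. That makes the compliant sample more distant from Day 168, and so more likely to lose to any unscheduled sample taken during the illness. The mapping can therefore discard the sample that the protocol protects and keep one that it would not have wanted.

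At stake is the control status, which decides whether a dose reduction counts in full or is set to 0%. A sample suppressed by sick-day hydrocortisone can read as controlled in a subject who has lost control. The same status decides response for the second key secondary endpoint, tested at 0.03. After Week 4, sick-day use may depend on how far the usual dose has been cut, so balance between arms cannot be taken for granted.

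**Working it through.** **Plan's own figure.** The documents give no figure on this point. The arm sizes of 110 and 55 come from SAP 3.3. The power stated there (above 90% for effect size 0.55 with 165 subjects) recomputes to 91.2% by the noncentral t and is not affected.

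**Step 1: which sample is chosen.** Take distance = |study day - 168|, smallest wins, earlier wins a tie. If the scheduled sample falls on Day 168 + k, an earlier sample displaces it when it lies between Day 168 - k and the day before the scheduled sample.
- Scheduled Day 170 (k = 2): displaced by Days 166 to 169.
- Scheduled Day 173 (k = 5): displaced by Days 163 to 172.
- Scheduled Day 174 (k = 6): displaced by Days 162 to 173. An unscheduled sample on Day 166 has distance 2 against 6 and is chosen.
- Scheduled on or before Day 168: no earlier sample can displace it.

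Day 174 lies beyond the ±5-day visit window, but the 3-day rule permits it. It is inside the SAP window because open-label drug starts that evening.

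**Step 2: effect on one subject.** Endpoint if controlled = (Week 24 dose / baseline dose - 1) × 100. If the dose fell but control was lost, the endpoint is 0%. Doses are assumptions, in mg/m²/day. The shift in the arm mean is the endpoint divided by the arm size.

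| Baseline | Usual Week 24 dose | Scored if falsely controlled | Shift, arm of 110 | Shift, arm of 55 |
|---|---|---|---|---|
| 17 | 9 | -47.1% | 0.43 | 0.86 |
| 18 | 10 | -44.4% | 0.40 | 0.81 |
| 14 | 9 | -35.7% | 0.32 | 0.65 |
| 25 | 10 | -60.0% | 0.55 | 1.09 |

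In each row the Week 24 dose is at or below 11, so the subject also turns from non-responder to responder: 1/110 = 0.9 or 1/55 = 1.8 percentage points of the response rate.

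**Step 3: the dose, conditionally.** Protocol Appendix B's lower sick-day amount is 30 mg/day. With an assumed body surface area of 1.8 m², that is 30/1.8 = 16.7 mg/m²/day. If it were counted on the sample date, the first row would score (9 + 16.7)/17 - 1 = +51%. This needs sick-day doses to be on the glucocorticoid eCRF and to be read into the endpoint dose. The false-control result needs them left out. One subject cannot show both, and the two errors run in opposite directions.

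**Step 4: Week 4.** The same rule applies around Day 28: a scheduled visit on Day 30 is displaced by Days 26 to 29. But SAP 6.3.4 uses the pre-dose sample, which Protocol 9.3.2 plans only at paired-sample visits, and doses are held stable to Week 4. Exposure is low.

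**The case against.** The strongest reply is that several things must coincide. The unscheduled sample must be of the post-dose type, fall nearer Day 168, be drawn under sick-day dosing and change the control status. That is fair and limits the frequency, but each condition is plausible, since illness is an obvious reason for an unscheduled sample. The selection sentence in SAP 6.7 also goes on to speak of summary tables and to allow exceptions. That does not rescue the primary endpoint, because the same section ties the Week 24 androstenedione date to the mapping and SAP 6.3.3 adds no sick-day condition.

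The averaging of Weeks 20 and 24 in SAP 9.3.4 and the deviation review in SAP 7.2 soften the problem. Neither changes the primary rule.

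Four stronger readings are tempting and not supported:
- *Sick-day doses will be scored as part of the endpoint dose.* Protocol 9.3.1 converts the usual regimen, SAP 13 does not list dropping that as a deviation, and how sick-day doses are entered on the eCRF is not stated.
- *The protocol bars every sample within 3 days of sick-day dosing.* It says should, and speaks of scheduled panels only. Unscheduled samples were never covered.
- *The diary is discarded.* Not being summarized does not prevent its use to identify affected samples.
- *The treatment effect is biased in favour of crinecerfont.* Neither frequency by arm nor net direction can be obtained from the documents.

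**Conclusion.** The gap is real and narrow. As written, SAP 6.7 can select an unscheduled post-dose androstenedione sample drawn under sick-day dosing over a Week 24 sample delayed in line with the protocol, and the error passes to the primary and responder endpoints. One misclassified subject moves by about 47 points under the assumed doses (36 to 60 across the range shown), or 0.43 to 0.86 points of an arm mean. No trial-level figure can be given, because the number of affected subjects is unknown. The dose side needs only a restatement of the protocol. Week 4 androstenedione is a key secondary endpoint and little exposed. The correction should be made because a stated rule can give the wrong answer and the remedy is cheap; the documents do not show that the primary result would be unreliable.

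**What to change.** 1. **SAP 6.7.** Before window mapping for androstenedione control at Week 24, make ineligible any hormone sample taken during sick-day dosing, or before the protocol's 3 days back on the regimen, as identified from the eDiary or eCRF. Use the closest eligible sample in the window. If none remains, treat androstenedione as missing under SAP 16.1. Apply the same condition to baseline, since control is judged against it, and to Week 4 for consistency.
2. **SAP 9.3.3.** Add a sensitivity analysis that keeps the excluded samples. Excluding data after a post-randomization event, then imputing on-drug subjects from same-arm completers, has its own risk of bias.
3. **SAP 9.3.2.** State, in line with Protocol 9.3.1, that only usual-regimen records enter the glucocorticoid daily dose.

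The cost is SAP wording and programming on data already collected; a few subjects may move to imputed values. An analysis of total steroid actually taken over the 28 days before Week 24 would answer a different question. It is optional and not needed to correct this error.
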